1.2. Schema

1.3. Schedule of Activities (SoA)

	Procedure	Pre-screening ¹	Screening ¹	Treatment															
				0	1	2	3	4	5	6	7	8	9	9a	10	11	12	13	14
Visit		0	up to 28 ±7 days prior to Day 1	1	29	57	85	113	141	169	197	204 (±1day)	225	253	281	309	337	365	28 ±7 days post last dose
Study Day (visit window ±7 days)				0	4	8	12	16	20	24	28	29	32	36	40	44	48	52	
Week																			
Screening/baseline	Informed consent	X																	
	Blood collection for eosinophils eligibility confirmation (if required) ²	X																	
	Inclusion and exclusion criteria		X																
	Demography		X																
	Full physical exam including height and weight		X																
	Medical history (includes substance usage and family history of premature CV disease CRSwNP/ECRS and asthma therapy, asthma and exacerbation history and concomitant medications)			X															
	SAE Review			X															
	History of HIV and Hep B, Hep C screen				X														
	Past and current medical conditions including cardiovascular medical history					X													
	History of systemic CS use for NP					X													
	History of NP surgery						X												

	Procedure	Pre-screening ¹	Screening ¹	Treatment																	
				0	1	2	3	4	5	6	7	8	9	9a	10	11	12	13	14	15	
Visit	Study Day (visit window ± 7 days)		up to 28 ± 7 days prior to Day 1	0	1	2	3	4	5	6	7	8	9	9a	10	11	12	13	14	15	IP DISC / EW Visit
Study Day (visit window ± 7 days)						1	29	57	85	113	141	169	197	204 (± 1 day)	225	253	281	309	337	365	28 ± 7 days post last dose
Week						0	4	8	12	16	20	24	28	29	32	36	40	44	48	52	
	Parasitic screening ³					X															
	Screening 12-lead ECG					X															
	Screening Vital signs					X															
	Assessment of endoscopic NP score ¹¹					X															
	Assessment of VAS for NP symptoms including Overall VAS ⁶					X															
	Assessment of Screening CT ⁴					X															
	Screening Laboratory assessments: Haematology (including blood eosinophils) and chemistry (including liver chemistries)					X															
	Screening Urinalysis					X															
	Urine pregnancy test (WOCBP only) ⁵					X															
	Dispense and Train in the use of eDiary ⁶					X															
	Register visit	X	X	X	X	X	X	X	X	X	X	X	X		X	X	X	X	X	X	
	Randomisation					X															
	Genetics sample ⁷														X						
Efficacy	Assessment of NP Surgery					X	X	X	X	X	X	X	X		X	X	X	X	X	X	
	Assessment of systemic CS and antibiotics dose and duration for NP					X	X	X	X	X	X	X	X		X	X	X	X	X	X	

	Procedure	Pre-screening ¹	Screening ¹	Treatment																	
				0	1	2	3	4	5	6	7	8	9	9a	10	11	12	13	14	15	
Visit				up to 28 ±7 days prior to Day 1	1	29	57	85	113	141	169	197	204 (±1day)	225	253	281	309	337	365	28 ±7 days post last dose	
Study Day (visit window ±7 days)					0	4	8	12	16	20	24	28	29	32	36	40	44	48	52		
Week																					
	VAS symptom score for nasal obstruction, nasal discharge, mucus in the throat, loss of smell, facial pain ⁶																				
	Overall VAS symptom score ⁶																				
	SNOT-22 ^{8, 9, 17}				X	X	X	X	X	X	X				X			X	X		
	SF-36 ^{8, 9, 10}				X	X							X						X	X	
	WPAI-GH ^{8, 9, 10}				X	X							X						X	X	
	ACQ – 5 ^{8, 9, 17}				X	X	X	X	X	X	X				X			X	X		
	Endoscopic NP score ¹¹				X	X	X		X		X				X	X		X	X		
	Assessment of CT ^{4, 5}																		X	X	
	Asthma exacerbation ¹²				X	X	X	X	X	X	X	X			X	X	X	X	X	X	
	Blood for PK ¹³					X							X	X ¹³					X	X	
	Blood for Immunogenicity				X								X						X	X	
Safety	AE/SAE review				X	X	X	X	X	X	X	X			X	X	X	X	X	X	
	Concomitant medication review (including INCS)				X	X	X	X	X	X	X	X			X	X	X	X	X	X	
	12-lead ECG				X							X							X	X	
	Vital signs (HR and BP)				X	X	X	X	X	X	X	X	X		X	X	X	X	X	X	
	Laboratory assessments: Haematology (including blood eosinophils) ¹⁵				X	X	X				X	X			X	X	X	X	X	X	
	Laboratory assessments: chemistry (including liver chemistries) ¹⁶				X	X	X				X				X	X		X	X	X	

	Procedure	Pre-screening ¹	Screening ¹	Treatment																
				0	1	2	3	4	5	6	7	8	9	9a	10	11	12	13	14	15
Visit				up to 28 ±7 days prior to Day 1	1	29	57	85	113	141	169	197	204 (±1day)	225	253	281	309	337	365	28 ±7 days post last dose
Study Day (visit window ±7 days)					0	4	8	12	16	20	24	28	29	32	36	40	44	48	52	
Week																				
	Urinalysis				X	X										X			X	X
	Urine pregnancy test (WOCBP) ⁵				X	X	X	X	X	X	X	X			X	X	X	X	X ⁵	X ⁵
	Dosing with study Drug/Placebo ¹⁴				X	X	X	X	X	X	X	X			X	X	X	X	X	
	eDiary Compliance Check				X	X	X	X	X	X	X	X			X	X	X	X	X	X
	eDiary Collection																		X	X
	Early withdrawal, intervention discontinuation																			X

1. Pre-screening and screening can be performed on the same day
2. A documented blood eosinophil count of >2% in the 12 months prior to Visit 0 OR through a blood sample taken between Visit 0 and Visit 1. ALL participants must meet blood eosinophil count of >2% by Visit 1
3. Parasitic screening is only required in countries with high-risk or for participants who have visited high-risk countries in the past 6 months. Sites should use local laboratories
4. A CT scan should be performed anytime during the run-in period up to a week prior randomisation. A second CT scan should be performed at V15 or IP discontinuation/Early Withdrawal visit (up to 14 days prior to the nominal study visit)
5. Urine Pregnancy test results to be assessed at all visits and prior to CT scan at Screening, V15 or IP discontinuation/Early Withdrawal Visit. If a urine test cannot be confirmed as negative (e.g., an ambiguous result), a serum pregnancy test is required.
6. eDiary completion by participants will be daily every morning between Screening Visit and Visit 15 (or IP discontinuation/Early Withdrawal Visit)
7. Genetics informed consent to be obtained any time prior sampling, Genetics sampling to be performed anytime while on treatment (Genetics sampling not applicable for participants in China)
8. Performed using eDiary device
9. All questionnaires will be performed before any other assessments on each particular visit, VAS scores (if not already completed at home), SNOT-22, (ACQ-5), SF-36 and WPAI. ACQ-5 should only be performed in Asthmatic participants. Order of questionnaires will be detailed in the Study Reference Manual.
10. SF-36 and WPAI will be performed at visits Baseline, week 4, week 24 and week 52 (or IP discontinuation/Early Withdrawal Visit) only
11. For endoscopic NP scores performed at V1, 3, 4, 6, 8, 10, 12, 14, 15 (or IP discontinuation/Early Withdrawal Visit), the nasal endoscopy assessment may be performed up to 3 days prior to the day of dosing but must not exceed the protocol defined windows of ±7 days from the nominal study visit. For V2, the endoscopic NP score cannot be performed earlier than V2 but must be performed at V2 upon completion of all screening procedures and prior to administration of IP.

12. For asthmatic participants only. An asthma exacerbation is defined as worsening of asthma requiring systemic corticosteroids (i.v. or oral steroid) for at least 3 days or a single IM CS dose and/or emergency department visit, or hospitalisation
13. Blood for PK will be collected at Visits 3 (pre-dose), 9 (pre-dose) and 15 (or IP discontinuation/early withdrawal). In addition, one post-dose PK collection will be at Week 29 (Visit 9a, one week after dose at Visit 9) with a collection visit allowance of ± 1 day. As for Week 29, blood sample will be collected from up to approximately first 30 Japanese and all Chinese participants randomised, no PK samples will be collected outside Japan and China
14. For participants who are willing to perform self-administration within the Japanese participants cohort: self-administer from Week 32 onwards (after receiving at least two trainings by investigator or delegate beforehand)
15. Laboratory assessments: Haematology (including blood eosinophils) will be taken at visits 1, 2, 3, 4, 7, 8, 10, 13, 14, 15 (or IP discontinuation/Early Withdrawal Visit)
16. Laboratory assessments: chemistry (including liver chemistries) will be taken at visits 1, 2, 3, 4, 7, 10, 13, 15 (or IP discontinuation/Early Withdrawal Visit)
17. ACQ-5 and SNOT-22 will be performed at baseline (visit 2), 3, 4, 5, 6, 7, 8, 11, 15, IP discontinuation/Early Withdrawal Visit

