7. DISCONTINUATION OF STUDY INTERVENTION AND PARTICIPANT DISCONTINUATION/WITHDRAWAL

At the point of informed consent prior to screening, participants will be requested to provide permission and agree to be contacted even after study withdrawal/ IP discontinuation to collect information relating to any surgical intervention to the NP. Every effort will be made to have all participants attend study visits up to Week 52 even if they discontinue study treatment in order to capture NP scores, symptom score, any subsequent surgical procedures or entry into a waiting list for NP surgery.

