7.1.4. IP Discontinuation Visit

Prematurely discontinuation of study treatment will be defined as any participant who is randomised to blinded medication and, for any reason, does not receive study treatment at Visit 14 (Week 48).

A participant may discontinue from study treatment at any time at his/her own request, or at the discretion of the investigator. Participants who discontinue from study treatment prematurely (for any reason) should, where possible, continue to be followed-up as per protocol until the completion of the Week 52 Visit assessments.

Participants that discontinue from study treatment should return to the clinic 4 weeks after the last dose for an IP Discontinuation Visit. If possible, at the IP Discontinuation Visit, the following evaluations and procedures should be completed and recorded in the eCRF as required:

- Concomitant medication assessment
- Adverse event assessment
- 12 -lead ECG
- Physical examination (recorded in source documents only)
- Vital signs
- Collect/review electronic diary
- Urine pregnancy test - for all WOCBP
- Assessment of endoscopic nasal polyp score
- Assessment of surgery
- Assessment of systemic CS use
- Assessment of INCS use
- Assessments of symptoms
- Assessment of HRQoL
- WPAI
- PK (Japan and China only)
- Lab assessments including liver chemistry and immunogenicity

- CT scan
- Assessment of asthma exacerbations
- Collection of eDiary
- Access the RAMOS NG to report participant's IP discontinuation visit from the study

After completion of the IP Discontinuation Visit, in cases where the participant cannot attend subsequent study visits in person telephone visits may be performed.

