8.2.3. Individual Symptoms Visual Analogue Scale (VAS)

All VAS to be used in the study will be administered using the eDiary and will be collected daily in the morning from screening to the end of the study period.

Every day, the participant will be asked to indicate on a VAS the severity of 6 nasal polyposis symptoms (one VAS for each symptom) and symptoms overall:

Please rate your “_____” at its worst over the previous 24 hours.

1. nasal obstruction; 2. nasal discharge; 3. mucus in the throat; 4. loss of smell; 5. facial pain; 6. overall VAS symptoms score.

The left-hand side of the scale (0) represents “[CCI](#)” and the right-hand side of the scale (100) represents “[CCI](#)”. Participants will be instructed on how to use the scale prior to using the scale.

VAS measure a characteristic or attitude that is believed to range across a continuum of values and cannot easily be directly measured. The participant selects a point on the line that represents their current state on the continuum. In this study symptom VAS will be collected using an eDiary, suitably pixilated to allow the selection of all integers from 0 to 100. A number of publications which shows the applicability of VAS administered electronically and comparability to traditional paper [[Hollen, 2013](#); [Reips, 2008](#); [Cook, 2004](#); [Jamison, 2002](#)]. VAS scores will be analysed using a 0 and 10 scale reported to 1 decimal point.

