
Endpoint	Statistical Analysis Methods
	
impacted by COVID-19 related events will not be included in the statistical analyses and will be treated as missing data..
 
d) Surgery, which includes any procedure involving instruments resulting in incision and removal of tissue from the nasal cavity (e.g. polypectomy) – to be handled using a composite strategy by incorporating occurrence of the event into the definition of the endpoint. Specifically, participants who undergo surgery will be assigned the worst possible score for the endpoint from the day of surgery onwards for inclusion in the analysis.
 
e) Course of systemic CS for CRSwNP / ECRS – to be handled using a treatment policy strategy. Data collected following a course of systemic CS for CRSwNP / ECRS will be included in the analysis where systemic CS will be considered as SoC treatment.
 
f) Interruption to IP of 2 or more consecutive doses – to be handled using a treatment policy. These events will be recorded as protocol deviations and participants are expected to continue IP per-protocol after interruption. Data collected will be included in the analysis regardless of IP interruption.
 
Any changes to the estimand strategy arising as result of unforeseen local or worldwide events will be documented in the Statistical Analysis Plan prior to unblinding of the study.
 
Independent reviewers, blinded to treatment, grade the total endoscopic nasal polyp score from image recording of endoscopies. The total score is reported as the sum of the right and left nostril scores and ranges from 0 to 8, with higher scores indicating greater disease severity.
 
Participants rate individual symptoms including nasal obstruction daily on a visual analogue scale (VAS) using an eDiary on a line with 101 individually selectable points ranging from 0 (none) to 100 (as bad as you can imagine). The final VAS scores for inclusion in summary and analysis tables will be derived from the electronically captured score by dividing each score by 10, and therefore will range from 0 to 10.
 
Total endoscopic nasal polyp score is collected at each clinical visit, the primary assessment will be at week 52 (centrally read data). Nasal obstruction is collected daily throughout the study via eDiary. Nasal obstruction at Week 52 will be calculated as the mean of all measurements made in the 4 weeks prior to the visit. The mean VAS score over the last 7 days before Visit 2 will be used to determine the baseline value.
 
For the co-primary analyses the change from baseline value for participants with surgery will be based on the worst possible score for the endpoint from the day of surgery onwards. Missing data due to study withdrawal, intercurrent events due to the COVID-19 pandemic or missing data for another reason will be assumed to be missing at random (MAR).
 
The comparison of mepolizumab with placebo will be expressed as a difference in mean change from baseline presented with corresponding 95% confidence intervals and associated p-value. The analysis will be performed for each co-primary endpoint using a mixed model repeated measures (MMRM) analysis, with covariates of treatment group, baseline score, log of baseline blood eosinophil count, background INCS use ,country and time point, plus interaction terms for time point by baseline value and time point by treatment group.

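### The protocol contradicts itself on whether the daily VAS diary continues after IP is stopped; if the schedule is followed, those participants have no evaluable Week 49–52 score for a co-primary endpoint

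*Protocol*

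**What the plan says.** **Passages that end the diary when IP stops**

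- Protocol 1.3, SoA footnote 6: "eDiary completion by participants will be daily every morning between Screening Visit and Visit 15 (or IP discontinuation/Early Withdrawal Visit").
- The SoA row "eDiary Collection" is marked twice, at Visit 15 and in the combined IP discontinuation/early withdrawal column.
- Protocol 7.1.4 lists "Collection of eDiary" among the procedures for the IP Discontinuation Visit, in addition to a combined collect-or-review item. On timing it says "Participants that discontinue from study treatment should return to the clinic 4 weeks after the last dose for an IP Discontinuation Visit"; the SoA gives 28 ± 7 days.

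**Passages that need the diary to continue**

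- Protocol 7 asks for attendance to Week 52 "even if they discontinue study treatment in order to capture NP scores, symptom score".
- Protocol 8.2.3 says the VAS "will be collected daily in the morning from screening to the end of the study period".
- Protocol 9.4.1: "Nasal obstruction is collected daily throughout the study via eDiary". SAP 4.2.1.2 says the same of all the symptom scores.
- Protocol 7.1.1 and 7.1.4 want IP stoppers followed per protocol through the Week 52 assessments.

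**Analysis rules that depend on the answer**

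- Stopping IP for reasons unrelated to COVID-19 is handled by treatment policy, and SAP 4.2.2 says the off-treatment data will be used.
- SAP 4.2.1.2 derives a 4-week mean only with at least 3 evaluable weeks, each with at least 4 diary days.
- SAP 4.2.3 imputes withdrawals from the pattern seen in participants who stopped IP but stayed in the trial.

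**The concern.** The IP Discontinuation Visit is not an exit visit. Section 7.1.4 plans further visits after it, and Section 7.2.2 describes participants who continue off treatment once it is done. If the device is handed in there, a participant who remains in follow-up has no means of recording the daily VAS, and no passage says it is kept or reissued.

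Three things are at stake, for participants who stop IP for non-COVID reasons, have no surgery and stay in the study:

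- Their Week 49–52 nasal obstruction score (H2) would be absent by design. So would the overall, composite and loss-of-smell VAS scores (H3, H5, H7).
- The MMRM would treat these values as missing at random, relying on the participant's own earlier scores and on patterns that are largely on treatment. That is not what a treatment-policy estimand asks for. If benefit fades off drug, the error favours mepolizumab.
- The sensitivity analysis meant to test this would have almost no measured off-treatment VAS to fit.

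Diary days that were never recorded cannot be recovered afterwards.

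**Working it through.** **1. The plan's own power figures.** Inputs from protocol 9.2: 80 per arm, two-sided 5%, SD 3.25 (VAS) and 1.82 (NP score), true differences 2.00 and 1.00. A two-sample t-test with 158 df gives:

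- VAS: smallest significant difference = t × 3.25 × √(2/80) = 1.01; power 97.2%.
- NP score: smallest significant difference = t × 1.82 × √(2/80) = 0.57; power 93.2%.

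Both agree with the plan.

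**2. Diary coverage if the SoA and 7.1.4 are followed.** Premature discontinuation means a participant who "does not receive study treatment at Visit 14 (Week 48"). The latest possible last dose is therefore Visit 13, Day 309 (± 7). The diary ends 28 ± 7 days later. With Visit 15 on Day 365, Weeks 49–52 are taken as the 28 days before it, Days 337–364.

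| Last dose | Diary ends | Visit 15 | Diary days in window | Evaluable weeks (3 needed) |
|---|---|---|---|---|
| Day 309 | 309 + 28 = 337 | 365 | 1 | 0 |
| Day 309 | 309 + 35 = 344 | 365 | 8 | 1 |
| Day 316 (+7) | 316 + 35 = 351 | 365 | 15 | 2 |
| Day 316 (+7) | 351 | 358 (−7) | 22 | 3 |
| Day 288 (Visit 12, +7) | 288 + 35 = 323 | 358 (−7) | 0 | 0 |

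Setting each of the three windows to −7, 0 or +7 gives 27 combinations for a last dose at Visit 13. Only one reaches 3 evaluable weeks, and it also needs the period to be anchored to the actual Visit 15. In general the diary must cover 7 + 7 + 4 = 18 days of the window and the nominal schedule covers 1, so the shifts must add up to at least 17 of a possible 21 days. A last dose at Visit 12 or earlier gives 0 days under every combination.

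**3. Off-treatment VAS for the imputation.** SAP 4.2.3 counts a visit as off treatment when it falls more than 28 days after the last dose. At most 35 − 28 = 7 diary days can fall after day 28. A 4-week mean needs at least 3 × 4 = 12.

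**4. Possible size of the bias.** The documents give neither a discontinuation rate nor a loss of effect off drug, so both are assumed. Bias = share of the mepolizumab arm affected × fraction of effect lost × 2.0:

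- 3–10% affected (about 2–8 of 80), 50–100% lost: 0.03 × 0.5 × 2.0 = 0.03 to 0.10 × 1.0 × 2.0 = 0.20 points, or 1.5–10% of the effect.
- 5–15% affected, same loss: 0.05 × 0.5 × 2.0 = 0.05 to 0.15 × 1.0 × 2.0 = 0.30 points.

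These figures lean high for the shares assumed, because the MMRM also uses each participant's earlier scores.

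**5. Power.** At a true difference of 1.8 (10% affected, all effect lost), protocol Table 1 gives 93.6%. At 1.7 (15% affected) the t-test gives 90.8%.

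**The case against.** The strongest reply is that footnote 6 uses stock wording for a combined SoA column. Similar wording appears in the footnotes for endoscopy and SNOT-22, where nobody reads it as ending assessment, and the SoA also has a diary compliance check at dosing visits and the final visit. That weakens footnote 6 taken alone. It does not explain why the device is collected at a visit after which participants are expected to stay in the study. Protocol Section 8 also makes adherence to the SoA a requirement of study conduct.

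Other points stand in part:

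- The harm depends on site practice. The Study Reference Manual may settle the matter, but it is not among the documents.
- The exact 4-week periods are left to the Output and Programming Specification, so Days 337–364 is the nominal reading.
- A participant who misses Visits 13 and 14 as an interruption meets the definition of discontinuation but may have no IP Discontinuation Visit, and so might keep the diary.
- The SAP labels off-treatment status by visit. A 4-week mean at a day 29–35 visit could therefore be evaluable and count as off treatment. It would consist mostly of days within 28 days of the last dose, so it says little about scores after drug effect is lost.
- SNOT-22 is completed on a diary device, but at the site (protocol 8.1.5.2). It is not part of this point.
- The bias is small under the assumed rates, and its direction depends on benefit fading. The other co-primary, NP score, is unaffected.

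**Conclusion.** The concern holds, with high confidence in the contradiction and in the day count. Followed as written, the SoA and Section 7.1.4 leave IP stoppers with 0 evaluable weeks out of the 3 required at nominal timing. Late windows give 1 or 2, and 3 only at the extreme edge of all three windows. The treatment-policy estimate for a co-primary endpoint and its planned sensitivity analysis would then lack the data they are defined on. That makes it a must-fix.

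The size of the bias is illustrative: 0.03–0.20 VAS points, or 0.05–0.30 on the wider assumption. It rests on assumed discontinuation and loss of effect, and on sites following the schedule. The issue is the validity of the estimate, not power. It does not extend to participants with surgery (assigned the worst score), COVID-related discontinuations (set to missing by plan), endoscopic NP score or SNOT-22.

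**What to change.** Reconcile the passages by amending three places in the protocol: SoA footnote 6, the SoA diary collection row, and the diary items in Section 7.1.4. The amended text should say that:

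- participants who stop IP but remain in the study keep the eDiary and complete the daily VAS to Visit 15;
- at the IP Discontinuation Visit the diary is reviewed, not collected;
- the device is collected only at Visit 15 or at withdrawal from the study.

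Section 7.2.2 waives the Early Withdrawal Visit for anyone who has already had an IP Discontinuation Visit, so the site memo should say how the device is returned in that case.

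The cost is three wording changes, a site memo and a small extra diary burden for the participants concerned. No procedure or participant is added, and neither dosing nor clinical care is affected.
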